All subjects who receive SUBLOCADE (including those who wish to discontinue early), will be encouraged to attend the EOT visit 28 days after SUBLOCADE administration (Day 29). After enrolment, available treatment options for completed subjects will be discussed. Any subject with ongoing AEs or concomitant medications at the EOT and has not continued medication for OUD (MOUD) will also be followed up by phone 2 weeks later for the End of Study (EOS) visit (Day 43) to assess the ongoing AEs or concomitant medications only.

Subjects who discontinue from the study before TM buprenorphine administration will be considered screen failures and will not be required to complete an EOT visit.

Subjects who discontinue from the study after TM buprenorphine administration, and before SUBLOCADE administration, will not be required to complete an EOT visit and will be contacted via telephone 24 to 72 hours after TM buprenorphine administration to assess any ongoing AEs and concomitant medications only.

| | |
|----------------------------------|--|
| Key Endpoints: | 
Number and percentage of subjects who experience any precipitated withdrawal within approximately 1 hour after SUBLOCADE administration (defined as an increase in COWS by ≥ 6 from the pre-SUBLOCADE value).
 
Number and percentage of subjects with ≥ 6 point-increase in COWS within the first 6, 12, 24, or 48 hours post SUBLOCADE administration.
 
Area under the curve (AUC) of COWS score from the time of administration of SUBLOCADE (i.e., time 0) through 6, 12, 24 and 48 hours after SUBLOCADE administration.
 
Total score on the COWS during the treatment period (i.e. at each assessment timepoint from administration of TM buprenorphine at Day 1 through EOT)
 
Score on the OC-VAS during the treatment period
 |
| Exploratory Endpoints: | 
Number and percentage of subjects who experience precipitated withdrawal from TM buprenorphine (defined as an increase in COWS by ≥ 6 from prior to the most recent dose of TM buprenorphine before SUBLOCADE administration).
 
Peak and overall plasma exposure to NMP following a single SC injection of 300 mg SUBLOCADE.
 |

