All subjects who receive SUBLOCADE (including those who wish to discontinue early), will be encouraged to attend the EOT visit 28 days after SUBLOCADE administration (Day 29). After enrolment, available treatment options for completed subjects will be discussed. Any subject with ongoing AEs or concomitant medications at the EOT and has not continued MOUD will also be followed up by phone 2 weeks later for the End of Study (EOS) visit (Day 43) to assess the ongoing AEs or concomitant medications only.

Subjects who discontinue from the study before TM buprenorphine administration will be considered screen failures and will not be required to complete an EOT visit.

Subjects who discontinue from the study after TM buprenorphine administration, and before SUBLOCADE administration, will be contacted via telephone 24 to 72 hours after TM buprenorphine administration to include assessment of AEs and concomitant medications only.

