 9. A sub-set of serum chemistry to be performed including: ALP, ALT, AST, bilirubin, albumin, total protein, GGT and LD only. For increased LFTs, subject should be asked to return to the clinic for weekly repeat liver chemistry testing (ALP, ALT, AST, and total bilirubin) until resolved, stabilised or return to within baseline values, per Section 8.2.7.3.
 10. Required for female subjects of childbearing potential only.
 11. Qualitative test to be performed for all visits. Additional quantitative test to be performed on Day 1. Additional unscheduled UDS may be performed as necessary.
 12. Details subjects illicit drug use, in addition to report question capturing frequency, route and date of last use.
 13. Injection site will be evaluated for signs of attempted removal. Any injection site reactions or infections will be recorded as AEs.
 14. A 2-mL blood sample will be collected for NMP PK analysis.
 15. Subjects will receive counselling during the study as determined by local standard of care.
 16. All subjects who receive SUBLOCADE (including those who wish to discontinue early), will be encouraged to attend the EOT visit 28 days after SUBLOCADE administration (Day 29). After enrolment, available treatment options for completed subjects will be discussed.
 17. Any subject with ongoing AEs or concomitant medications at the EOT visit and is not continuing MOUD will also be followed up by phone 2 weeks later for the EOS visit (Day 43) to assess the ongoing AEs or concomitant medications only.
 18. Subjects who discontinue from the study and have been administered TM buprenorphine but have not been dosed with SUBLOCADE will be followed up via telephone within 24 to 72 hours to assess ongoing AEs and concomitant medications only.
-

AE=adverse event; ALP=alkaline phosphatase; ALT=alkaline aminotransferase; AST=aspartate aminotransferase; BMI=body mass index; BUP=buprenorphine; COWS=Clinical Opiate Withdrawal Scale; ECG=electrocardiogram; GGT=gamma-glutamyl transferase; PK=pharmacokinetics; OC-VAS=Opioid Craving Visual Analogue Scale; LD=lactase dehydrogenase; LFT=liver function test; TLFB=TimeLine Follow Back; TM=transmucosal; UDS=urine drug screen; VAS=Visual Analogue Scale

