6.4 TM Buprenorphine Treatment and Early Termination

When an eligible subject's COWS is ≥ 8 and all pre-buprenorphine assessments have been completed, the subject will receive TM buprenorphine. Subjects experiencing precipitated withdrawal will be treated for withdrawal symptoms. If precipitated withdrawal occurs before SUBLOCADE administration, the TM induction may be restarted later on the same day at the discretion of the Investigator, based on the half-life of the opioid reported on the TLFB. Alternatively, the Investigator may permit the subject to return to the facility on another day (within the Screening Period). Returning subjects will repeat all Day 1 scheduled assessments.

A subject will be considered a TM Buprenorphine Early Termination if he/she is dosed with TM buprenorphine but is not dosed with SUBLOCADE. Reasons for early termination (e.g., withdrawal of consent, AE of precipitated withdrawal, allergic/hypersensitivity to buprenorphine) will be recorded in the eCRF. Subjects who discontinue from the study after TM buprenorphine administration and before SUBLOCADE administration, will be withdrawn from the study and contacted via

telephone 24 to 72 hours after TM buprenorphine administration to assess ongoing AEs and concomitant medications only.

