6.7 Withdrawal and Stopping Criteria

6.7.1 Subject Withdrawal from the Study

If the subject has permanently discontinued study treatment (including depot removal) and is no longer being followed for study assessments and procedures (including follow-up procedures), he/she will be considered withdrawn from the study. The primary reason for withdrawing from the study must be entered into the eCRF (e.g., subject is lost to follow-up, Investigator terminates the study or Investigator's discretion).

Subjects who discontinue from the study before TM buprenorphine administration will be considered a screen failure and will not be required to complete an ET or EOT visit.

Subjects who discontinue from the study after TM buprenorphine administration, and before SUBLOCADE administration will not be required to complete an EOT visit but will be contacted via telephone 24 to 72 hours after TM buprenorphine administration to assess AEs and concomitant medications only.

All subjects who receive SUBLOCADE (including those who wish to discontinue early), will be encouraged to attend the EOT visit 28 days after SUBLOCADE administration (Day 29), as well as the EOS visit via telephone (Day 43).

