5.1.4 Definition of Analysis Phases

Screening phase: starts from the date of screening visit and ends at the date/time of the first TM-BUP dose for induction.

Induction phase: starts from the date/time of the first TM-BUP dose for induction and ends at the date/time of SUBLOCADE injection or TM-BUP ET visit.

SUBLOCADE treatment phase: starts from the date/time of SUBLOCADE injection through the date of last visit in the study (EOT or EOS, whichever is applicable).

The overall treatment period for the study is the combination of induction and SUBLOCADE treatment phases.

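### The 24 to 72 h call to subjects given TM buprenorphine but not SUBLOCADE covers ongoing AEs in four places and AEs in three, so AEs starting after departure may be missed

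*Protocol*

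**What the plan says.** Seven places in the current text describe the same call.

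Four restrict it to ongoing events:
- Protocol Study Summary: "to assess any ongoing AEs and concomitant medications only".
- Protocol 4.3, Table 1 footnote 18: "will be followed up via telephone within 24 to 72 hours to assess ongoing AEs and concomitant medications only".
- Protocol 6.4: "telephone 24 to 72 hours after TM buprenorphine administration to assess ongoing AEs and concomitant medications only".
- SAP 1.3, Table 3 footnote 18, which repeats the Protocol footnote.

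Three do not:
- Protocol 4.1: "to include assessment of AEs and concomitant medications only".
- Protocol 6.7.1: "contacted via telephone 24 to 72 hours after TM buprenorphine administration to assess AEs and concomitant medications only".
- The running text of SAP 1.3, which matches Protocol 4.1.

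The surrounding rules are these. Protocol 6.7.1 and the Study Summary do not require an EOT visit from subjects who stop between TM buprenorphine and SUBLOCADE. Protocol 10.3 collects AEs from consent to completion of the EOT visit. SAP 5.1.4 says that the induction phase "ends at the date/time of SUBLOCADE injection or TM-BUP ET visit". SAP 5.5.2 summarises TEAEs, serious TEAEs and related TEAEs on the TM BUP Analysis Set, with a separate summary for events whose start falls in the induction phase.

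**The concern.** The restricted wording ends in *only*, so a site could take it as the full content of the call. An AE that began after the subject left the clinic would then not necessarily be asked about, and no later visit would pick it up. The SAP assigns AEs to the induction phase by start date and time, and for these subjects it keeps that phase open until the early-termination contact. The planned table would therefore cover a period for which the collection instruction is unclear.

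The trial's sole objective is safety and tolerability, and Protocol 3.3 counts TEAEs from TM buprenorphine onward. The reasons listed in Protocol 6.4 for stopping at this stage include precipitated withdrawal and hypersensitivity, as well as withdrawal of consent. For the first two in particular, later events are of interest.

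**Working it through.** No formula in the plan bears on this point, and the plan gives no figure to reproduce. The check is a comparison of texts.

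**Step 1. Count the statements of scope.**

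| Place | AEs covered by the call |
|---|---|
| Protocol Study Summary | ongoing |
| Protocol Table 1 footnote 18 | ongoing |
| Protocol 6.4 | ongoing |
| SAP Table 3 footnote 18 | ongoing |
| Protocol 4.1 | AEs |
| Protocol 6.7.1 | AEs |
| SAP 1.3 text | AEs |

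The Protocol divides 3 to 2. With the SAP added, the division is 4 to 3. Each document contradicts itself. None of these statements comes from an amendment log.

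**Step 2. Ask whether a general rule resolves it.** Protocol 10.3 is not limited to ongoing events, which favours the broader reading. But its end point is the EOT visit. Subjects who stop before SUBLOCADE need not attend one, so for them 10.3 gives no end of collection and does not say what the call must ask.

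**Step 3. Ask what each reading of *ongoing* would miss.**

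| AE starting after departure | Read as open at departure | Read as present at the call | Unrestricted wording |
|---|---|---|---|
| Still present at the call | not asked | asked | asked |
| Resolved before the call | not asked | not asked | asked |

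An event that starts and resolves between departure and the call falls outside both readings of the restricted wording.

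**Step 4. Compare with the analysis.** Under SAP 5.1.4 and 5.5.2, both rows of the table in step 3 hold events with a start time inside the induction phase. Both belong in the induction-phase summaries on the TM BUP Analysis Set. Only the unrestricted wording collects both.

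**Step 5. Ask what can be said about size.** Let N be the number of subjects in the TM BUP Analysis Set and k the number of them who never receive SUBLOCADE. A missed event lowers a percentage by 1/N if the subject has no other event in that category, and by 0 if the subject is already counted there. The plan gives about 15 subjects dosed with SUBLOCADE. It gives neither k nor N. If k = 0, nobody is affected. The share of the 24 to 72 h spent outside the clinic is also unknown: eligibility for SUBLOCADE is assessed one hour after TM buprenorphine, but no discharge time is stated for subjects who are not injected.

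**The case against.** The best defence is that the plan, read as a whole, already asks for these events. Protocol 10.3 collects AEs from consent, Protocol 10.2 requires AEs to be reported whether volunteered or solicited, and three descriptions of the call carry no restriction. Moreover, *ongoing* may mean present at the time of the call. Footnote 17 on the Day 43 call refers back to events open at EOT, and footnote 18 has no such back-reference. For hypersensitivity, Protocol 4.1 and SAP 1.3 also mention a call at 24 to 72 h with no limit on its content. After precipitated withdrawal, induction may be restarted or the subject may return and repeat the Day 1 assessments, so the call is not the only later contact for everyone whose first induction fails.

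Much of this stands. A reader might infer that new AEs in these subjects certainly go uncollected, or that the TEAE counts are biased low. The documents do not support either. A site may follow the broader wording, and a subject stopped for an AE of precipitated withdrawal is already in the any-TEAE numerator.

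A reader might also suppose 15 to 20 enrolled, and conclude that each missed subject moves a percentage by 1/20 = 5 to 1/15 = 6.7 points. That enrolment range is not in the documents. If 15 were enrolled and all 15 dosed, no subject would be affected at all. Likewise, a short clinic stay that leaves nearly the whole window uncovered is not stated anywhere.

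What the defence does not remove is the conflict itself, or the gap for events resolved before the call. Whether the AE row of Protocol Table 1 extends to the early-termination column cannot be read from the extracted text, so it is not relied on here.

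**Conclusion.** The inconsistency is real and present in both documents. For subjects who receive TM buprenorphine, do not receive SUBLOCADE and discontinue, the call is the only scheduled later contact, and its content is described in two incompatible ways. AEs starting after departure may be missed if a site follows the restricted wording; those resolved before the call are the most exposed.

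The reach is limited. The key endpoints use the FAS and the main safety tables use SUBLOCADE recipients, so neither is touched. The exploratory TM buprenorphine endpoint rests on COWS, not AEs. Only the additional AE summaries on the TM BUP Analysis Set are affected, by an amount that cannot be stated from the documents.

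The conclusion rests on one assumption: that some sites or call scripts would treat the *ongoing* wording as the instruction to follow. It is worth correcting because the written rule conflicts with a planned safety table and the correction is small.

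**What to change.** Delete *ongoing* from the description of this call in the Protocol Study Summary, Protocol Table 1 footnote 18, Protocol 6.4 and SAP Table 3 footnote 18. All seven places would then agree that the call records AEs that are new, ongoing or resolved since TM buprenorphine. Correcting only the Protocol would leave the SAP footnote in conflict with it.

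Add a sentence to Protocol 10.3 stating that, for subjects who receive TM buprenorphine but not SUBLOCADE and discontinue, AE collection runs to this call. That matches the end of the induction phase in SAP 5.1.4. Align any call script with the same wording.

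The cost is four one-word deletions and one added sentence. No further contact, visit or analysis is required.

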1. Upon arriving at the clinic, subjects will provide a urine sample for a UDS for qualitative and quantitative analysis, a urine sample for a pregnancy test (child-bearing females only), perform an alcohol breathalyser test and self-report their concomitant medications since screening and recent illicit drug use (including the use of a TimeLine Follow Back [TLFB]). If subject is deemed eligible for check-in the subject will then be assessed for withdrawal symptoms using COWS and for craving using OC-VAS.
 2. Details subjects illicit drug use, in addition to report question capturing frequency, route and date of last use.
 3. Required for female subjects of childbearing potential only.
 4. Per Investigator's discretion, subjects with positive test may either remain in the clinic or be re-scheduled to return on another date.
 5. Per Investigator's discretion, subjects with COWS <8 may either remain in the clinic and repeat assessments at a later time or be re-scheduled to return on another date. The COWS may be repeated at any time, per Investigator's discretion, and should always be repeated just before TM-BUP and SUBLOCADE administration. The OC-VAS should be performed each time a COWS assessment is performed.
 6. If the subject is asleep at 16 and 20 hours, the assessments will not be performed, and the reason should be noted in the CRF.
 7. Includes a review of any previous (taken since screening) and ongoing medications (including over-the-counter) and herbal supplements.
 8. Includes systolic and diastolic blood pressure, pulse rate, respiratory rate and oral temperature after the subject has been in a sitting position for ≥ 3 minutes.
 9. An ECG will be collected after the subject has been in a supine position for ≥ 5 minutes.
 10. Eligible subjects must meet the buprenorphine dosing criterion, prior to receiving 4mg TM buprenorphine.
 11. A sub-set of serum chemistry to be performed including: ALP, ALT, AST, bilirubin, albumin, total protein, GGT and LD only. For increased LFTs, subject should be asked to return to the clinic for weekly repeat liver chemistry testing (ALP, ALT, AST, and total bilirubin) until resolved, stabilised or return to within baseline values, per Section 8.2.7.3.
 12. Weight to be captured; BMI will be calculated in the database using height from screening.
 13. Assessment to be performed anytime pre-SUBLOCADE dose.
 14. Eligible subjects meet SUBLOCADE dosing criteria, prior to receiving SUBLOCADE.

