8.2.5 Physical Examination

A complete physical examination will be conducted by the Investigator or a medically qualified sub-Investigator at screening and EOT (Table 1). This examination will include an assessment of general appearance, skin and extremities, head and neck, lymph nodes, eyes, ears, nose, throat, thyroid, neurological system, lungs, cardiovascular system, and abdomen (liver and spleen). The examination will not include a breast, pelvic or rectal exam, unless clinically indicated.

If any clinically significant change from screening is noted, it will be reported as an AE and followed to resolution or until reaching a stable endpoint. Details of the physical examination will be recorded in the source document.

Weight (kg) will be assessed as per the schedule of assessments in Table 1 and Table 2. Height (cm) will be recorded at screening only.

The SUBLOCADE injection site will be evaluated for signs of attempted depot removal. Any removals will be reported as an AE of special interest as directed in Section 10.1. Any injection site reactions or infections will be recorded as AEs. Injection site evaluations will be performed according to the schedule of assessments, as shown in Table 1 and Table 2.

8.2.6 *Sedation VAS*

For this study, the Sedation VAS is a horizontal line, using a 100-millimetre (mm) scale anchored by word descriptors at each end: “Not at all” (0 mm) to “Almost asleep” (100 mm). The subject will mark the point on the line that he/she feels represents his/her perception of the current state of sedation at the time. The VAS score is calculated as the difference from the left-hand end of the line to the point that the subject marked.

The subject will complete a VAS question for sedation as per the schedule of assessments in Table 1 and Table 2.

The Sedation VAS responses will be recorded on paper source by the subjects and will then be entered into the subject’s eCRF by the site.

8.2.7 *Clinical Laboratory Tests*

Clinical laboratory tests will be performed in a licensed clinical laboratory. Urine pregnancy tests may be performed using a licensed test (dipstick). Subjects are to be in a sitting/supine position during blood collection.

The following clinical laboratory tests (Table 3) will be performed according to the schedule of assessments, as shown in Table 1 and Table 2.

Table 3 List of Laboratory Tests

| Screening Only | Serum Chemistry: | Pregnancy: |

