5.3.8 COWS Total Score Absolute Value and Change - Main Analytical Approach

The absolute value and change in COWS total score will be summarized using descriptive statistics at each scheduled nominal timepoint. The summary for COWS values will start from the Day 1 Check-in timepoint for the last TM BUP dose in the induction phase through EOT. The summary for change in COWS total score from the Pre-TM BUP value or from the Pre-SUBLOCADE value will start from the first scheduled nominal timepoint post the last TM BUP dose in the induction phase or the SUBLOCADE injection through EOT.

The analysis will use observed data and will include subjects with the pre-TM BUP/pre-SUBLOCADE value and a COWS assessment at the scheduled timepoint of interest.

The mean COWS total scores (absolute value and change from pre-TM BUP and pre-SUBLOCADE) will be plotted over time for all scheduled timepoints.

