5.3.11 OC-VAS Score Absolute Value and Change - Main Analytical Approach

The absolute value and change in the OC-VAS score will be summarized using descriptive statistics. The summary for OC-VAS scores will start from the Day 1 Check-in timepoint for the last TM BUP dose in the induction phase through EOT. The summary for change in OC-VAS score from the Pre-TM BUP value or from the Pre-SUBLOCADE value will start from the first scheduled nominal timepoint post the last TM BUP dose in the induction phase or the SUBLOCADE injection through EOT.

The analysis will use observed data and will include subjects with at least one pre-TM BUP/pre-SUBLOCADE OC-VAS assessment and an OC-VAS assessment at the timepoint of interest.

The mean OC-VAS scores (absolute value and change from pre-TM BUP and pre-SUBLOCADE) will be plotted over time for all scheduled timepoints.

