5.5.7 Sedation VAS

At each time point, absolute value and change from the pre-SUBLOCADE Baseline of Sedation VAS will be summarised using observed data.

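### COWS, OC-VAS and Sedation VAS results at 16 and 20 hours describe awake subjects only, but the SAP summarises them like any other timepoint

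*Protocol*

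**What the plan says.** The detailed injection-visit schedule carries this rule in a footnote (Protocol 4.3, footnote 6 to Table 2): "If the subject is asleep at 16 and 20 hours, the assessments will not be performed". Sites are asked to record why in the CRF. In SAP Table 4, which sets out the same visit, the footnote mark sits on the 16 and 20 hour cells of the COWS and OC-VAS row and of the Sedation VAS row, and nowhere else.

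The SAP then handles the three scales as follows.

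- **COWS (5.3.8).** "The absolute value and change in COWS total score will be summarized using descriptive statistics at each scheduled nominal timepoint". On missing scores: "The analysis will use observed data and will include subjects with the pre-TM BUP/pre-SUBLOCADE value and a COWS assessment at the scheduled timepoint of interest". On figures, means "will be plotted over time for all scheduled timepoints".
- **OC-VAS (5.3.11).** Observed data again, and "The mean OC-VAS scores (absolute value and change from pre-TM BUP and pre-SUBLOCADE) will be plotted over time for all scheduled timepoints".
- **Sedation VAS (5.5.7).** "At each time point, absolute value and change from the pre-SUBLOCADE Baseline of Sedation VAS will be summarised using observed data". The SAP text specifies no mean plot for this scale; table and figure specifications are in a separate document (SAP 1).

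The visit mapping in SAP Appendix 3 gives 16 and 20 hours the same status as the other nominal times. No planned table or figure uses the recorded reason for a skipped assessment, although the general data listings under SAP 5.1.5 should carry it.

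**The concern.** Whether a score exists at these two times depends on whether the subject is awake, and wakefulness is not neutral for any of the three scales.

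The Sedation VAS is a 100 mm "scale anchored by word descriptors at each end: “Not at all” (0 mm) to “Almost asleep” (100 mm") (Protocol 8.2.6). A sleeping subject is at or past the upper end and gives no score for that reason. For COWS and OC-VAS the link is indirect: Protocol 4.1 lists insomnia among the withdrawal symptoms that may be treated, so subjects still awake may be those with more withdrawal.

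COWS and OC-VAS scores at each timepoint are key endpoints (Protocol 3.1), and sedation is a named safety assessment (Protocol 3.3). The sponsor added the 16 and 20 hour assessments by amendment. They lead up to the 24 hour buprenorphine peak cited in Protocol 1.2.7. If 16 and 20 hour means from awake subjects are joined to 12 and 24 hour means that are not restricted in this way, a change in who is measured can be read as a change over time. The SAP version history recognises that missing COWS scores may be informative, but its response is adjudication of precipitated withdrawal (SAP 5.3.3.2), which does nothing for the mean profiles.

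**Working it through.** **Inputs.** The planned number is 15 (Protocol 14.2). The plan's own figure for that number reproduces: 1 − 0.90^15 = 0.794, the stated 79.4%. It has no bearing on this point. The documents give no share of subjects asleep, no SD for the scales, and no association between wakefulness and score. All three are assumed below.

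**How often sleep is likely.** Subjects arrive in the morning (Protocol 4.1). If the injection is given between 09:00 and 12:00 (assumed), 16 hours falls at 01:00 to 04:00 and 20 hours at 05:00 to 08:00. Some sleep is to be expected, as the footnote itself anticipates.

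**COWS and OC-VAS.** Let p be the share awake and ρ the correlation between a latent tendency to be awake and the score, both normal. With c = Φ⁻¹(1 − p), the mean in awake subjects exceeds the all-subject mean by ρ·φ(c)/p standard deviations. For p = 0.5 and ρ = 0.5 this is 0.5 × 0.399/0.5 = 0.40 SD.

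| Share awake | Expected n of 15 | ρ = 0 | ρ = 0.2 | ρ = 0.5 | ρ = 0.7 |
|---|---|---|---|---|---|
| 90% | 13.5 | 0 | 0.04 | 0.10 | 0.14 |
| 70% | 10.5 | 0 | 0.10 | 0.25 | 0.35 |
| 50% | 7.5 | 0 | 0.16 | 0.40 | 0.56 |
| 30% | 4.5 | 0 | 0.23 | 0.58 | 0.81 |

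The formula is linear in ρ, so a negative correlation of the same size reverses the sign.

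**Sedation VAS.** As a convention for a sensitivity figure, place sleepers at the top of the scale. With awake mean m, the all-subject mean is p·m + (1 − p)·100, while the planned table shows m.

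| Share awake | All-subject mean, m = 20 mm | Gap | All-subject mean, m = 40 mm | Gap |
|---|---|---|---|---|
| 90% | 28 mm | 8 mm | 46 mm | 6 mm |
| 70% | 44 mm | 24 mm | 58 mm | 18 mm |
| 50% | 60 mm | 40 mm | 70 mm | 30 mm |
| 30% | 76 mm | 56 mm | 82 mm | 42 mm |

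**What is not affected.** The key timepoints are 1, 6, 12, 24 and 48 hours (SAP 5.3), and Kaplan-Meier censoring depends only on those (SAP 5.3.2, Table 7). A score missing at 16 or 20 hours censors nobody. A rise of 6 points or more at those hours still counts as an event when scored, though it can be seen only in a subject who is awake.

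**Why the scores should be kept.** On the nominal 12, 16, 20 and 24 hour grid, the trapezoid weight of each of the two points is 4 hours, 8 hours together: 8/24 = 33% of the 0 to 24 hour AUC and 8/48 = 17% of the 0 to 48 hour AUC. For a sleeper with no other score in between, the SAP interpolates that stretch from the 12 and 24 hour scores.

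**The case against.** The strongest reply is that these are ordinary sleeping hours. If most missing scores reflect normal night sleep, the awake subjects may differ little from the rest on COWS and craving, and the bias may be near zero. The direction is also open: the list that names insomnia gives diphenhydramine and trazodone for it (Protocol 4.1), so some subjects with treated withdrawal may be asleep because they were treated, which would pull the awake mean down. Both points stand for COWS and OC-VAS.

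A reader might infer that the curves will show a false withdrawal bump and a sedation dip just before 24 hours. The documents do not support that. For COWS and OC-VAS, wakefulness is only a correlate of the score, and neither sign nor size can be derived. For sedation, the SAP text plans no mean plot on which a dip could appear. The VAS also records the subject's own perception and defines no score for a sleeper, so understatement is a possibility and the 100 mm figures are a convention.

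It is also fair that the analyses are descriptive, without hypothesis tests (SAP 2); that individual COWS and OC-VAS plots are planned (SAP 5.3.9 and 5.3.12); and that Protocol 14.5.5 gives n for the Sedation VAS. Those outputs let a careful reader see that scores are absent. They do not tabulate how many subjects were asleep rather than missed, and no individual Sedation VAS plot is specified.

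Dropping the two means altogether would be hard to defend, since these assessments were added on purpose. Labelling answers the problem without discarding them.

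**Conclusion.** The concern holds in a limited form. Followed as written, the SAP reports awake-only values at 16 and 20 hours with nothing to say so. For Sedation VAS the selection is on the measured variable itself, and the mean could understate sedation: by 8 to 56 mm if the awake mean is 20 mm, sleepers are placed at 100 mm, and 90% to 30% are awake. For COWS and OC-VAS the selection is on a correlate. The mean could be biased, plausibly upward, by 0 to about 0.8 SD for correlations of 0 to 0.7 over the same awake shares, but the documents settle neither direction nor amount.

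The event-rate estimates at the key timepoints are not invalidated by this rule. It is a presentation fault in descriptive summaries, worth correcting because two of the three scales are key endpoints, the group is small, and the data needed are already collected.

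**What to change.** Amend SAP 5.3.8, 5.3.11 and 5.5.7 for the 16 and 20 hour timepoints:

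- Tabulate the number assessed, the number asleep (from the reason in the CRF) and the number missing for other reasons.
- Show asleep as a separate Sedation VAS category beside the scores of awake subjects.
- Label any mean or change from baseline at these times as awake subjects only.
- In the COWS and OC-VAS mean plots, show the 16 and 20 hour means unconnected to those at 12 and 24 hours.
- Keep every score taken at these times for the event of a rise of 6 points or more, the AUC and the individual plots.

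The assessment schedule does not change and no new data are needed. The cost is slightly more table work and a broken line at two plotted timepoints.
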